Traditional designs—whether client-randomized or site-randomized—were not viable due to statistical power, contamination risk, and the dual focus on intervention and implementation outcomes. For instance, randomizing clients would risk contamination within sites, and randomizing sites would drastically restrict power. This

is addressed by the proposed stepped-wedge design,²⁵⁻²⁷ with all sites participating in a baseline period (Standard Implementation), experiment period (Enhanced Implementation), and post-experiment period (Observation). Blocks of sites are randomized to the *timing* of the experiment period. Because intervention condition *changes over time*, the intervention effects reflect within-block changes (e.g., between the Enhanced and Standard periods). The design is highly flexible and maximizes power, and the proposed analyses straightforwardly accommodate different data structures for client-services outcomes (Aim 1) and implementation process outcomes (Aim 2), clients that span periods, and outcomes that are both research- and site-collected.

Data structure. For Aim 1, the *client-services outcomes* are structured with repeated visits (level-1) that are nested within clients (level-2) who are nested within periods (level-3) that are nested within sites (level-4). However, for analysis, the outcomes will reflect a single status for each client (e.g., initiation of PrEP), reducing the data to a three-level structure. For Aim 2, the *implementation process outcomes* are structured with three repeated measurements (i.e., across the baseline, enhanced, and observation periods; level-1) that are nested within sites (level-2). In each case, the small number of sites will be addressed. Of note, across aims, supplementary time-to-event analyses^{28, 29} (e.g., the effect of Standard Implementation on time to client awareness) are possible by reformulating the data to client- and site-period structures. Likewise, clients will be associated with the period in which the outcome status is finalized.

Model building, estimation, and significance testing. The nested data structures will be evaluated using mixed-effects regression models, but with 8 sites, specialized methods are required to estimate and validate the effects.^{29,30} Model estimation will utilize Bayesian Markov chain Monte Carlo (MCMC) methods.²⁷ With this approach, the results are based on a large number of replications, providing an empirically-based sampling distribution—rather than a single point estimate—for each model parameter (e.g., the effect of Enhanced Implementation). Further, the conclusions will be validated using a frequentist, fixed effects approach (i.e., dummy-coded indicators) to control for site effects.³¹ To test for within-block changes across the three periods, two dummy-coded indicators will be included to differentiate the Enhanced and Observation periods from the reference Standard period. Continuous, dichotomous, and ordered categorical outcomes will be evaluated according to Gaussian, binomial, and ordinal distributions. To evaluate the magnitude and precision of effects, 95% CIs will be computed, along with odds ratios (ORs) for non-linear outcomes. The Bayesian MCMC models will be implemented in MLwiN,²⁷ and single-level regression models will be implemented in R.³²

Evaluation of Specific Aim 1: To evaluate whether the addition of SIC-guided PrEP delivery (Enhanced Implementation) to standard health system PrEP delivery improves services outcomes, including: awareness, screening, offer, initiation, and continuation at 6 months. Although the outcomes are repeatedly monitored, each reflects a client-level status. The three-level mixed-effects regression model, with clients (level-1) within periods (level-2) within sites (level-3), will include control variables for client characteristics (e.g. age, partnership status, ethnicity [Han vs other], sexual identity) and site characteristics (e.g. staffing, collaboration history between VCT and

STI clinics, institutional leadership, localized epidemiology), along with indicators for study periods. Additionally, to control for temporal effects—natural improvements in PrEP implementation over time—for each client, the models will control for the time of study entry using linear and quadratic polynomials for the number of months from the start of the Standard period. With a single outcome status for each client, this controls each client's outcomes for the timing of participating during the site's PrEP implementation process. The results will indicate the average within-block change from Standard to Enhanced in the log-odds of awareness, screening, offer, initiation, and continuation. Likewise, to determine whether the effects are maintained, outcomes from the Sustainment period will be compared to the Standard and Enhanced periods.

Statistical power for Aim 1. Multilevel power analysis typically assumes interventions are at the level of individuals or groups. However, here, the intervention is time-varying. As such, power for the primary client-services level outcomes was estimated using a multi-step approach recommended by Hox³³:

First, the *total sample* of observations was computed. For client-services level PrEP outcomes (ie, awareness, screening, offer, initiations, continuation), the sample size calculation reflects the size of the site client population and the availability of donated TDF/FTC (minimum of 1064 PrEP initiators). We anticipate ~2600 MSM clients per site per year and estimate ~133 PrEP initiators per site. However, this sample size is nested, introducing dependency and decreasing the level of statistical power.

Second, to penalize the total sample for nesting, the design effect formula is reorganized (i.e. $n_{\text{eff}} = n/[1+\{n_{\text{clus}}-1\}]$) to provide the effective sample size of independent observations. Using a conservative nesting effect (i.e. =0.25 for phases/sites), the

observations provide statistical power equivalent to 32 independent observations.

Despite the large number of MSM clients each year, the effective sample reaches an upper limit of 32 due to (a) the small number of sites and (b) the large cluster size per site. However, the large cluster provides high reliability for estimated level-2 effects.

Third, the effective sample size is used in a conventional power analysis. The results indicated that power is .80 to detect an effect of OR = 3.3 for the effect of Standard Implementation on client services outcomes. This is equivalent to a medium-to-large standardized effect of $d=0.66$, or a between-period difference in probability of 29%. For a less conservative nesting effect ($=0.10$), the sample is sufficient to detect OR=2.0, or a 16% between-period difference.

Evaluation of Specific Aim 2: To compare the time, costs, and resources required for Standard versus Enhanced PrEP implementation. The expected opportunity cost of implementation for sites will be modeled using an estimator that will identify the “best practice” implementation costs. The theoretical model assumes that sites attempt to minimize costs of implementation in order to maximize excess revenue subject to a standard economic production function. **This production function supports a dual cost function: where C_{it} represents the SIC-measured implementation costs for the i^{th} program in the t^{th} phase, X_{it} are characteristics of program i in phase t , is an i.i.d. error term, is a one-sided error term corresponding to the technical inefficiency for the i^{th} practice in phase, and represents the coefficients of the best practice (most efficient) cost function. We assume the best-practice cost function is of the CobbDouglas form, such that the log-linear transformation yields.**

With estimates of the model parameters, we will predict the best practice implementation costs and technical inefficiency costs for each program. We will also explore which program characteristics and contextual factors are associated with higher or lower estimated inefficiencies. We will include measures of the “best practice” implementation costs, technical cost inefficiency and intervention costs in a model predicting successful implementation. The aggregated cost variables will be added to linear probability models (because cost measures require a prediction substitution model) as covariates alongside SIC Duration and Proportion scores to predict the binary outcome of whether a program sustained a minimum of 1-year post Stage 8 of the SIC (Competency). Differences in use of resources will be examined between sites that sustain versus those that do not. The assessment and analysis of implementation costs will be critical for the government as they develop their plan for widespread scale-up.

Implementation outcomes. For Aim 2, with the focus on implementation process outcomes (rather than client services outcomes), the data are structured with three periods (level-1) within sites (level-2). The outcomes include the proportion of implementation activities completed, duration of activity completion, maximum implementation stage reached, and benchmarks on the Five-80s (3 consecutive months for implementation, 6 consecutive months for sustainment). The model will include key client and site characteristics, and dummy-coded indicators to differentiate the three periods. The results will indicate the difference between Enhanced and Standard in the level of each implementation outcome. As with Aim 1, the conclusions will be validated based on single-level models with fixed-effect control variables for site differences. Likewise, with the focus on achieving implementation process benchmarks, the model

will be extended to a time-to-event framework,²⁹ testing for differences between Enhanced and Standard in the time required to achieve benchmarks (adjusted for the duration of the Standard period). With the focus on implementation process outcomes, power for this aim is inherently limited. Results will focus on estimates of 95% CIs for the effect of Enhanced Implementation.

Attrition & Missing Data. Following intention-to-treat principles, sites will be retained in research measurement independently of participation in Enhanced Implementation.³⁴ Highly successful tracking and retention protocols will minimize missing data. However, some data will inevitably be missing. To address this, assumptions will be evaluated, and informed by the results, one of several approaches will be used³⁵: i) For a small proportion of missing data with evidence of Missing at Random (MAR), the data will be analyzed using the estimation procedures described above. ii) For a non-trivial amount of missing data and evidence of MAR, multiple imputation for repeated measurements will be used.³⁶ iii) For a non-random missing data mechanism, pattern mixture models will be used to identify and control the effect of the non-random mechanism.^{37, 38}

Data Analysis

Data analysis was informed by the Consolidated Framework for Implementation Research (CFIR). CFIR consolidates holistic factors determining the implementation and delivery of an intervention/innovation. Evidence shows that utilizing CFIR can lead to a better PrEP implementation design and a smoother PrEP service delivery to the target audience. We developed an Interview Guide and conducted initial data analysis based on the CFIR V1.0. Following updates to the CFIR in 2022, we applied CFIR V2.0

to develop an analytic matrix applied to the data to identify our key findings. We employed the Rapid Qualitative Analysis approach to analyze the data. Implementation studies show that rapid analysis can yield similar and consistent results while saving costs and resources. Data were first transcribed verbatim into Chinese and then translated verbatim to English for analysis. Four members of the research group split into teams of two, with each team reading the assigned transcripts and then summarizing the transcript into a two-page memo with a goal to reduce the data. An excel-based matrix template was developed with the CFIR domains, subdomains, constructs, and subconstructs listed in the rows and facilitators, barriers and solutions to overcoming barrier written as the column headers. After creating the matrix and arriving at consensus within the research team on the definition of each CFIR construct, text from transcripts was copied into the matrix. Teams met weekly to review matrix application and ensure consistency. Differences in application of matrix and interpretation of data were reconciled through discussion. Finally, two teams came together to discuss and name the most relevant barriers, facilitators, and solutions to overcoming barriers within each CFIR constructs.

References

3. Wendel K. Same Day PrEP in the STD Clinic: The Denver Public Health Experience. 2017. <http://www.ncsddc.org/wp-content/uploads/2017/11/Wendel-Same-Day-PrEP.pdf>. Accessed September 2nd, 2018.

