over 6 months. The study team set 80% targets for two reasons: 1) 80% targets are commonly used in observational facilitated training in implementation processes; 2) the PI's recently-published PrEP modeling analysis clearly showed the differential epidemiological impact a high real-world PrEP effectiveness would have compared to a low real world effectiveness: with 80% effectiveness, PrEP would lead to 345,000 infections averted over a 20-year horizon compared to 219,000 with 50% effectiveness and 87,900 with 20% effectiveness (Zhang et al., 2018), spurring the team to choose ambitious targets that could drive down infections among MSM. To examine the implementation process and efficiency of the Enhanced versus Standard implementation approaches we will use SIC and COINS tools to monitor sites for implementation process and resource use. Outcomes will include proportion of implementation activities completed, duration of each implementation phase, and cost and resource allocation for completion of each implementation phase (Aim 2). Based on robust studies that assess implementation using the SIC, *we hypothesize that time and resources spent in Pre-Implementation will be associated with higher odds of successful implementation and sustainment.*

Recruitment

All recruitment activities will take place at our international site (Yunnan, China) and will be conducted in Mandarin Chinese, the primary language of the region, by Chinese-speaking research staff. All research staff will complete the required human subject training before conducting any recruitment activities. All procedures related to recruitment have been reviewed and approved by Yunnan CDC IRB. Columbia personnel will not be involved in the recruitment of participants.

Two types of participants will be recruited for in-depth interviews in our study: (1) MSM clients of participating facilities; (2) program staff who are involved in PrEP implementation. We will conduct the interviews with clients and program staff in each study period, as a result, a total of four rounds of interviews will be conducted.

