All data will be in electronic format and we will not have any hard copy of study data. In general, we will use Secure Sockets Layer (SSL) encryption to securely transfer the study data that are in electronic format. We will store study data on password-protected, encrypted computers, and will restrict access to the data to key study personnel.

This study will analyze data from five different sources. Here is a detailed description of how we will ensure confidentiality and safely stored data from five different sources:

1. SIC and COINS data

Description: The PrEP-SIC data includes a log of implementation activities completed by each site along with the dates of activity completion (e.g.: date written PrEP implementation plan completed, date first PrEP user retained in care for six months). The COINS tool assesses direct and indirect expenses, including the number of hours per role expected in completing each implementation activity listed in the SIC. SIC and COINS data will be collected by our Yunnan-based research coordinator through phone call and in-person site visits at two to four-week intervals and entered

into the SIC website. SIC and COINS tool measures implementation process and does NOT contain personal identifiable information (PII) or protected health information (PHI).

2. PrEP M&E data

Description: Yunnan CDC (our primary collaborator in China and a subaward recipient on this grant) is upgrading their HIV prevention monitoring and evaluation (M&E) system to incorporate PrEP service delivery indicators. We expect this PrEP M&E data system to start working in May 2020, and it will document data including routine HIV utilization, PrEP service delivery and process measures for all facilities involved in PrEP implementation across the province and including at our study site. Yunnan CDC staff will extract data and aggregated at site level (e.g. number of HIV testing done per site, percentage of MSM clients receiving sexual health needs assessment, number of PrEP initiations). Only this site-level, aggregated data will be shared with the B-HAPPY study team.

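### COINS is described as recording expected hours per activity, but the Aim 2 cost and efficiency analyses need hours actually spent; if expected hours are used, labour differences may be understated

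*Combined protocol and SAP*

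**What the plan says.** Under Confidentiality of study data, item 1 (SIC and COINS data), the two tools are described together. The SIC part is "a log of implementation activities completed by each site along with the dates of activity completion". For cost, the text says "The COINS tool assesses direct and indirect expenses", "including the number of hours per role expected in completing each implementation activity listed in the SIC". The research coordinator in Yunnan collects both "through phone call and in-person site visits at two to four-week intervals".

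The Study Design section gives the purpose: "we will use SIC and COINS tools to monitor sites for implementation process and resource use". Its hypothesis is that "time and resources spent in Pre-Implementation will be associated with" better odds of success and sustainment.

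In the SAP, Aim 2 is "To compare the time, costs, and resources required for Standard versus Enhanced PrEP implementation". The SAP specifies a cost function indexed by program and phase, with an ordinary error term and a one-sided term for technical inefficiency, and then states that "we will predict the best practice implementation costs and technical inefficiency costs for each program". It attributes the cost variable to SIC and does not name COINS.

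**The concern.** Technical inefficiency is cost above best practice, so it has to be estimated from what sites really used. Expected hours are a plan or a norm. They need not include the time a site spends beyond expectation, and that excess is the labour part of the inefficiency term. The same gap affects the Standard versus Enhanced contrast: if an activity takes more or less staff time under Enhanced but the entry stays near the expected figure, the difference is lost or reduced.

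Costs and resources make up much of one of the two specific aims, and the SAP says that the government will rely on the cost results when planning scale-up. The SAP also concedes that power for the Aim 2 implementation process outcomes is limited, so there is little room for an input that dampens the contrast.

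**Working it through.** The documents give no cost figure, sample size or power calculation that depends on COINS hours, so there is no stated figure to reproduce. The check has two parts.

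**1. The sections side by side**

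- *Labour input as described* (Confidentiality of study data, item 1): expected hours per role, per SIC activity.
- *Labour input as needed* (Study Design; SAP, Evaluation of Specific Aim 2): resource use, resources spent, and program-by-phase cost with an inefficiency term. All are realised quantities.
- *Other possible sources of hours*: the same section lists four more data sources. The M&E extract holds site-level service data, the checklist is seven yes/no items for clients, and the client and staff interviews are qualitative. None is described as recording staff hours. SIC completion dates give calendar time, not labour.
- *What is not stated*: whether the expected hours are one reference value for everyone, or are obtained separately for each site and period.

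**2. How much the labour contrast could shrink**

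All inputs here are assumptions, since the documents give none. Take one activity that needs 10 hours under Standard, with equal wages. Let r be the true Enhanced/Standard ratio of hours, and b the share of the true difference that the expected hours follow. Recorded Enhanced hours are 10 + b × (10r − 10), so

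recorded ratio = 1 + b × (r − 1).

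| True ratio r | b = 0 (one shared reference value) | b = 0.5 | b = 1 (full tracking) |
|---|---|---|---|
| 0.80 | 1.00 | 1 + 0.5 × (−0.20) = 0.90 | 0.80 |
| 1.25 | 1.00 | 1 + 0.5 × 0.25 = 1.125 | 1.25 |
| 1.50 | 1.00 | 1 + 0.5 × 0.50 = 1.25 | 1.50 |

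The labour difference for the same activity disappears only in the first column. It is halved in the second and intact in the third.

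**3. What can still differ even with b = 0**

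- *Non-labour expenses.* If these are 25% higher under Enhanced and labour is a share s of Standard cost, the total-cost ratio is s + (1 − s) × 1.25. For s = 0.5, 0.7 and 0.9 this gives 1.125, 1.075 and 1.025. If actual hours had also risen by 25%, the true ratio would be 1.25 in each case.
- *Number of activities completed.* With equal hours per activity, completing 40 rather than 30 gives a phase labour ratio of 40/30 = 1.33.

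Total cost can therefore vary between periods whichever kind of hours is held. What is at risk is the labour part.

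**The case against.** The strongest reply is that this is a wording slip. *Expended in completing* would read more naturally. Collection every two to four weeks has little purpose for fixed planning values, and the stated aims refer to resource use and resources spent. The sentence also stands in a confidentiality section and is not an instruction for data collection; the COINS form and manual are not in the documents, so the form may already ask for actual hours. This is plausible, but the documents do not settle it. No other text says that actual hours are recorded, so clarification is needed on either reading.

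A reader might also infer that labour cost cannot differ between Standard and Enhanced, that inefficiency cannot be measured at all, or that labour cost must correlate perfectly with the number of SIC activities completed and so duplicate the SIC Proportion score. The documents do not support these readings. The first needs one expected value per activity shared by all sites and periods, which is nowhere stated; even then it holds only for the same activity at the same wages and role mix. The second ignores that hours are only one component of the expenses COINS covers. The third also needs equal hours and wages for every activity. Under a shared reference value labour cost would overlap with the SIC Proportion score, but the documents do not show how strongly.

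Two further points stand. The time part of Aim 2 rests on SIC completion dates and is untouched, as are the Aim 1 client-services outcomes. And rewording cannot recover actual hours for periods in which only expected hours were held.

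**Conclusion.** The point holds in conditional form. The one description of labour measurement does not match what the Aim 2 cost comparison and inefficiency model need. If expected hours are used, the Standard versus Enhanced labour-cost difference and the labour part of inefficiency are understated to the extent that expectations do not follow actual time: not at all with full tracking, by half with 50% tracking, and completely for the same activity only under a single shared reference value.

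The numbers are illustrative. The direction assumes that expected hours move the same way as actual hours but by no more. That is not guaranteed: SIC is observational at Baseline and also guides implementation under Enhanced, so Enhanced planning could itself change what staff expect.

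**What to change.** 1. In Confidentiality of study data, item 1, and on the COINS form if it reads the same way, define the labour field as hours per role actually spent on each activity, recorded by site and study period at the existing two-to-four-week contacts.
2. Keep expected hours, if wanted, as a separate field that does not enter the cost variable.
3. In the SAP, under Evaluation of Specific Aim 2, state that labour cost is computed from actual hours and name COINS as the source of the cost variable.
4. Establish what is already held. This version is effective 08/31/2023 and describes the interview analysis in the past tense, so COINS data may already exist. If actual hours were collected, correct the word. If only expected hours exist for past periods, say so and limit the labour-cost and efficiency conclusions for those periods.

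The cost is a field definition, a short SAP edit and slightly more recording at contacts that already take place. It will not recover actual hours for periods already past.
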